6.1.2 Continuous Variables

- Raw value and change from baseline in the following assessments:
 - o TJC (68 joints)
 - o SJC (66 joints)
 - o CRP
 - o ESR
 - o SGAP (VAS) (100 mm VAS)
 - o SGA (VAS) (100 mm VAS)
 - o PGA (VAS) (100 mm VAS)
 - o HAQ-DI (See Section 10.5 Appendix 5: Computation of HAQ-DI Score)
 - DAS28-CRP score
 - DAS28-ESR score
 - \circ SF-36v2[®]
 - o SDAI score
 - CDAI score
 - FACIT-Fatigue Score (only for subjects who transferred from study RAJ1. See
 Section 10.6 Appendix 6: Computation of FACIT-Fatigue Scale Score)
 - WPAI score (only for subjects who transferred from studies RAJ3 or RAJ4. See
 Section 10.7 Appendix 7: Computation of WPAI Scale Score)

6.2 Safety Variables

- AEs
- Vital signs (body temperature, pulse rate and blood pressure in sitting position)
- Body weight
- 12-lead ECG
- Chest radiography
- Laboratory assessments

6.3 Pharmacokinetic Variables

Refer to PK analysis plan.

6.4 Pharmacodynamic Variables

- Change from baseline for following variables in lymphocyte subset assays
- 1. Japan
 - o CD3+/Lymphocytes (%), CD3+ (cells/uL)
 - o CD8+/Lymphocytes (%), CD8+ (cells/uL)

- o CD4+/Lymphocytes (%), CD4+ (cells/uL)
- CD19+/Lymphocytes (%), CD19+ (cells/uL)
- CD4/CD8 Ratio
- o (CD16 or CD56)+/Lymphocytes (%), (CD16 or CD56)+ (cells/uL)
- (CD16+ and CD56+)/CD3- (%), CD16+ and CD56+ (cells/uL)
- (CD16- and CD56+)/CD3- (%), CD16- and CD56+ (cells/uL)
- (CD16+ and CD56-)/CD3- (%), CD16+ and CD56- (cells/uL)
- o (CD16- and CD56-)/CD3- (%), CD16- and CD56- (cells/uL)
- CD56 bright/CD3- (%), CD56 bright (cells/uL)
- o CD56 dim/CD3- (%), CD56 dim (cells/uL)

2. Korea

- o CD3+/Lymphocytes (%), CD3 (cells/uL)
- o (CD3+ and CD8+)/CD3+ (%), CD3+ and CD8+ (cells/uL)
- o (CD3+ and CD4+)/CD3+ (%), CD3+ and CD4+ (cells/uL)
- o (CD16 or CD56)+/CD3- (%), (CD16 or CD56)+ (cells/uL)
- o CD19+/CD3- (%), CD19+ (cells/uL)
- o CD4/CD8 Ratio
- o (CD16+ and CD56+)/CD3- (%), CD16+ and CD56+ (cells/uL)
- o (CD16- and CD56+)/CD3- (%), CD16- and CD56+ (cells/uL)
- o (CD16+ and CD56-)/CD3- (%), CD16+ and CD56- (cells/uL)
- o (CD16- and CD56-)/CD3- (%), CD16- and CD56- (cells/uL)

3. Taiwan

- o CD3+/Lymphocytes (%), CD3 (cells/uL)
- o (CD3+ and CD8+)/Lymphocytes (%), CD3+ and CD8+ (cells/uL)
- (CD3+ and CD4+)/Lymphocytes (%), CD3+ and CD4+ (cells/uL)
- (CD16 or CD56)+/Lymphocytes (%), (CD16 or CD56)+ (cells/uL)
- o CD19+/Lymphocytes (%), CD19+ (cells/uL)
- o CD4/CD8 Ratio
- (CD16+ and CD56+)/Lymphocytes (%), CD16+ and CD56+ (cells/uL)
- o (CD16- and CD56+)/Lymphocytes (%), CD16- and CD56+ (cells/uL)
- o (CD16+ and CD56-)/Lymphocytes (%), CD16+ and CD56- (cells/uL)

o (CD16- and CD56-)/Lymphocytes (%), CD16- and CD56- (cells/uL)

6.5 Other Variables

- Date of Last Dose of Study Drug:
 - If date of last dose of study is unknown, the date will be imputed by date of withdrawal.
- Duration of RA at baseline of preceding study (years), calculated as: (Date of Screening visit of preceding study Onset Date of RA +1) / 365.25, and then rounded to one decimal place. The onset date of RA doesn't have the day (e.g., 2013-03), therefore the first day of the month will be used (2013-03-01).
 - Missing onset date of RA will be imputed. For example, if month is missing (e.g., 2013), then the first day of January will be used (2013-01-01).
- Age at Week 0 (years), calculated as: integer part of (Date of Week 0 visit date of birth +1) / 365.25.
- Duration of exposure during RAJ2 (months)

Duration of exposure during RAJ2 will be calculated in days, using the following formula:

(('Date of Last Dose of Study Drug'* - 'Date of First Study Drug Taken at RAJ2'**) + 1)/30.4375

- *: DSLDT [End of Study-page of the CRF].
- **: EXSTDT [Date of First Study Drug Taken -page of the CRF]
- Treatment compliance during RAJ2 (%)

Treatment compliance will be based on number of tablets and calculated as follows:

Treatment compliance (%) =

[Total number of tablets actually received in the treatment period]

-----x 100

[Total number of tablets planned to receive in the treatment period]

Where total number of tablets planned to receive in the treatment period is calculated as below: ∑{(number of tablets per administration#) x (duration of administration##)} in ASP015K 50,100, 150 mg. It will be summed up to Date of Last Dose of Study Drug. #: refer to the table below; differ depending on the protocol version ##: summarized by dose level [ASP015K 50,100, 150 mg], by protocol version [Ver. 1.0, On and After Ver. 2.0]

Protocol Version	Ver. 1.0		On and After Ver. 2.0			
Dose per administration	50 mg	100 mg	50 mg	100 mg	150 mg	
Number of tablets per administration	3 tablets	4 tablets	1 tablets	1 tablets	1 tablets	

And total number of tablets actually received in the treatment period will be calculated as: (total number of tablets dispensed) – (total number of tablets returned) – (total number of tablets lost) up to Date of Last Dose of Study Drug. After study completion and data base is locked, all data will be used to calculate the compliance.

- Number of prior DMARD biologics, According to the preceding study
- Prior Biologic DMARD-IR, According to the preceding study

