
Test Drug  Mode of Administration:  Dose:  Duration of Treatment:
	
Test drug: ASP015K 10 mg and 30 mg tablets  Dose: (starting dose) 50 mg/day, (escalated dose) 100 mg/day  The starting dose will be 50 mg/day.  The dose may be increased to 100 mg QD will be permitted at the point in time as the following 2 conditions are met.
 
 
1) When the DAS28-ESR score is 3.2 or higher (corresponding to moderate disease activity or high disease activity) on the study visit day specified in the protocol (at 2 or more consecutive visit days up to Week 12)
 
2) When the investigator or sub-investigator judges there to be no problem with safety for the subject in the assessment performed on the study visit day on which the DAS28-ESR of 3.2 score or higher was exhibited
 
 
Moreover, after dose escalation, the dose may again be reduced from 100 mg/day to 50 mg/day at the discretion of the investigator or sub-investigator on the visit day specified in the protocol. The investigator or sub-investigator will decide whether or not to reduce the dosage on the basis of the following criterion.
 
 
• If an AE with an NCI-CTCAE grade classification of Grade 2 or higher has developed.
 
 
Mode of administration: To be orally administered QD after breakfast. The first dose should be given at each study center on the day of the Week 0 visit after all of the necessary assessments and tests have been completed.
 
Duration of treatment: Because this study will end at the point in time where the Phase III study begins, the duration of treatment will differ depending upon the subject (planned maximum duration of treatment: 132 weeks). To

- CONFIDENTIAL -

	prevent purposeless continuation of dosing without effect, the investigator or sub-investigator will assess each subject for efficacy and safety at each visit, confirm the appropriateness of continued administration for each individual, and decide whether or not to continue dosing.
Comparative drug Mode of Administration: Dose: Duration of Treatment:	Not applicable.

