7.3.2 Treatment Compliance

[Analysis Set: SAF]

Treatment compliance during RAJ2 will be examined for subjects in the SAF whose total study drug count and first and last days of treatment are known. These data will be summarized as below.

- Descriptive statistics for treatment compliance during RAJ2 will be presented.
- Treatment compliance during RAJ2 will be categorized according to the following categories:
 - o <50%
 - o 50% <75%
 - 0 75% <90%
 - 0 90% 100%

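### Treatment compliance is pooled in tablets across formulations of 3–4 tablets and 1 tablet a day, so it is misweighted towards the Ver. 1.0 period for RAJ1 subjects treated under both

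*SAP*

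**What the plan says.** SAP 6.5 states: "Treatment compliance will be based on number of tablets and calculated as follows". The numerator is "total number of tablets dispensed) – (total number of tablets returned) – (total number of tablets lost) up to Date of Last Dose of Study Drug". The denominator adds up "number of tablets per administration#) x (duration of administration" over the 50, 100 and 150 mg levels, and "It will be summed up to Date of Last Dose of Study Drug".

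Two footnotes qualify the denominator. The one on tablets per administration says: "refer to the table below; differ depending on the protocol version". Its table gives 3 tablets for 50 mg and 4 for 100 mg under Ver. 1.0, and 1 tablet at every dose from Ver. 2.0. The one on duration says: "summarized by dose level [ASP015K 50,100, 150 mg], by protocol version [Ver. 1.0, On and After Ver. 2.0".

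On reporting, SAP 7.3.2 plans descriptive statistics for the whole-study value and adds: "Treatment compliance during RAJ2 will be categorized according to the following categories". The categories are <50%, 50–<75%, 75–<90% and 90–100%. It lists no result by protocol version. Under SAP 7.1, summaries are shown by preceding study and overall, so the RAJ1 column stands beside RAJ3 and RAJ4.

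**The concern.** A compliance percentage is normally read as the share of scheduled doses that a subject took. A ratio of pooled tablets has that meaning only if a dose is always the same number of tablets. Here it is not, for RAJ1 subjects who started on the old tablets and continued on the new ones. A fully missed day costs 3 or 4 tablets in the early period and 1 tablet later.

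The study is meant to describe long-term administration, and for these subjects the formula gives the least weight per day to the later years. It also makes the RAJ1 column a different quantity from the RAJ3 and RAJ4 columns, where every day counts as one tablet.

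**Working it through.** **Inputs from the documents**

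- Tablets per daily dose: k = 3 (50 mg) or 4 (100 mg) under Ver. 1.0, and 1 from Ver. 2.0 (SAP 6.5 table).
- Tablet strengths under ver. 1.3 (Protocol Appendix 7, synopsis): "Test drug: ASP015K 10 mg and 30 mg tablets".
- Starting dose of 50 mg for everyone under ver. 1.3, with 100 mg only after escalation criteria were met (same synopsis).
- Planned maximum treatment under ver. 1.3: 132 weeks.

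**Inputs assumed**

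The documents give neither the time each subject spent on each version nor any compliance rate. I take T1 = 2 years on Ver. 1.0 and T2 = 5 years after, and vary this below. A total of 7 years is credible for the longest-treated subjects: the study was planned from February 2012, and the SAP has an exposure category above 84 months. Early and later compliance are c1 and c2.

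**1. Reproduce the SAP table.** The fewest 10 mg and 30 mg tablets making 50 mg are 30+10+10, which is 3. For 100 mg they are 30+30+30+10, which is 4. Both agree with the SAP.

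**2. Formulas.**

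- SAP ratio = (k·T1·c1 + T2·c2) / (k·T1 + T2)
- Ratio in daily doses = (T1·c1 + T2·c2) / (T1 + T2)

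**3. Weight of the early period (2 + 5 years).** By days it is 2/7 = 28.6%. In the SAP ratio it is 6/11 = 54.5% for k = 3 and 8/13 = 61.5% for k = 4. One year at each dose gives (3+4)/(3+4+5) = 7/12 = 58.3%. The k = 4 figure is an upper bound, because nobody started at 100 mg.

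**4. Effect on the reported figure (2 + 5 years).**

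| c1, then c2 | SAP, k = 3 | SAP, k = 4 | Daily doses | Category |
|---|---|---|---|---|
| 98%, 90% | 1038/11 = 94.4% | 1234/13 = 94.9% | 646/7 = 92.3% | unchanged (90–100%) |
| 98%, 60% | 888/11 = 80.7% | 1084/13 = 83.4% | 496/7 = 70.9% | 75–<90% instead of 50–<75% |
| 80%, 100% | 980/11 = 89.1% | 1140/13 = 87.7% | 660/7 = 94.3% | 75–<90% instead of 90–100% |
| 90%, 90% | 90.0% | 90.0% | 90.0% | unchanged |

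The error is the difference in weights times (c1 − c2). The weight difference is 0.545 − 0.286 = 0.26 for k = 3, and 0.615 − 0.286 = 0.33 for k = 4. A gap of 8 points therefore moves the figure by 2.1 to 2.6 points, and a gap of 38 points by 9.9 to 12.5.

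**5. Other splits of time.**

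| T1 + T2 | Early share of days | Early share of ratio, k = 3 | k = 4 |
|---|---|---|---|
| 1 + 6 years | 14.3% | 33.3% | 40.0% |
| 2 + 5 years | 28.6% | 54.5% | 61.5% |
| 132 weeks + 4 years | 38.7% | 65.5% | 71.7% |

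The early period makes up more than half of the ratio only if k·T1 > T2. That means more than 25% of treatment time for k = 3, or more than 20% for k = 4.

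**The case against.** The best defence is the footnote that mentions dose level and protocol version. It shows that the authors knew the tablet count had changed, and the detailed table specifications are not among the documents. But the footnote is attached to duration, so it tells the programmer how to tally duration before multiplying. Nothing in SAP 6.5 converts tablets to doses, and SAP 7.3.2 lists only the whole-study value.

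A reader might infer that the formula hides poor later compliance. The documents do not support that as a statement of fact. The formula has no built-in direction, and no compliance data are given for either period. Text can be found on both sides. Ver. 1.3 had a discontinuation rule for missed doses (7 or more in 4 weeks, later 21 or more in 12 weeks) that the current criteria lack, which makes a later decline plausible. On the other hand, Protocol 5.1.4 has tablet counts, renewed guidance and contact between visits, which makes a fall to 60% over five years an extreme case.

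A reader might also infer that the figure mostly describes the early period for all 201 RAJ1 subjects. That depends on the time split in the working above. The 201 are subjects entering the extension, and the number who went on to the new tablets is not stated. Anyone who stopped before then is unaffected.

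The consequence is limited too. Compliance defines no analysis set (SAP 5.1 to 5.3), is not an endpoint and enters no test. Exposure is computed separately, from dates.

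**Conclusion.** The misweighting is real and follows from the SAP's formula and table without any assumption: a Ver. 1.0 day counts 3 or 4 times a later day. It affects only RAJ1 subjects treated under both formulations and, through them, the overall column.

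Its size depends on assumed durations and rates. Under 2 + 5 years it is about 2 to 3 points, with no change of category, when compliance falls from 98% to 90%. It is about 10 to 12.5 points, with a change of category, when compliance falls from 98% to 60%. It is 5 to 7 points in the opposite direction when early compliance is 80% and later compliance 100%. It is zero when the two are equal.

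This is an error in a descriptive table. It does not undermine the efficacy or safety analyses. It is still worth correcting, because the table cannot be read as a share of doses for these subjects or compared across preceding studies.

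**What to change.** In SAP 6.5, within each dose level and protocol version, divide both tablets taken and tablets planned by the tablets per administration. Sum the resulting daily doses over levels and versions, and form the ratio from those sums. In SAP 7.3.2, also show compliance before and after Ver. 2.0 for RAJ1 subjects.

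The cost is a few lines of SAP text and one derivation step, with no new data. Planned duration is already split by dose level and version. The numerator can be split in the same way provided that tablet counts are held by dispensing or visit, which should be confirmed.

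A minor addition: tablets neither returned nor recorded as lost count as taken, so values above 100% are possible but have no category in SAP 7.3.2. Add one. Until then such values would show only through the maximum in the descriptive statistics.

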7 STATISTICAL METHODOLOGY

7.1 General Considerations

- For continuous variables, descriptive statistics will include the number of subjects (n), mean, standard deviation (SD), median, minimum, and maximum.
- For categorical variables: number and percentages of subjects will be described.
- For time-to-event variables: number and percentage of subjects with the event using Kaplan-Meier method, the cumulative event rate will be estimated and a plot will be constructed.
- All data processing, summarization, and analyses will be performed using SAS Drug Development (ver. 4.5), and PC-SAS (ver. 9.4) or higher versions.
- Specifications for table, figures, and data listing formats can be found in the TLF specifications for this study.
- For the definition of subgroups of interest can be referred to Section 7.8.
- Summaries based on FAS and SAF (e.g. disposition, baseline, efficacy data and safety data) will be presented by preceding studies and overall, unless specifically stated otherwise.
- Medical Dictionary for Regulatory Activities (MedDRA) 11.1 will be used as the coding dictionary for adverse event and medical history.
- Confidence interval for binary outcome is continuity corrected in all analysis.
- For the analyses of efficacy and pharmacodynamics variables in this extension study, values at the baseline in the preceding studies (RAJ1, RAJ3, and RAJ4) will be used as the baseline values. However, changes from baseline values of this extension study will also be examined where appropriate. For the analyses of safety, Week 0 of this extension study will be referred to as the baseline; however, changes from baseline values of the preceding studies (RAJ1, RAJ3, and RAJ4) will also be examined where appropriate.
- Change from baseline to post-baseline will be calculated as: post-baseline value baseline value. If the baseline value is missing, then that subject is not included in the calculation at any visit.
- Percent change from baseline to post-baseline will be calculated as: 100 × (change /baseline). If the baseline value is 0 or missing, or post-baseline value is missing, then percent change from baseline to post-baseline is missing.
- The values below the lower limit of quantitation (BQL) for β-D-glucan, hCG, Troponin, CK-MB will be treated as it is and these variables are not used for descriptive statistics

- and displayed in the listings. As for β -D-glucan, it is used for shift-from baseline analysis.
- If CRP value (mg/dL) is the lower or equal limit of quantitation (i.e. <0.01 mg/dL or =<0.01 mg/dL) then CRP is regarded as 0.01 mg/dL, and used for the calculation of DAS28-CRP, etc. and categorized in <0.01 mg/dL.
- If ESR value (mm/hr) is the upper limit of quantitation (i.e. >=100 mm/hr) then ESR is regarded as 100 mm/hr, and used for the calculation of DAS28-ESR.
- Treatment Sequence Set of preceding study will be used for the analysis by preceding study. This set takes into consideration the initial treatment groups (in RAJ1), a switch from placebo to active treatment at Week 12 (in RAJ3), and a switch from placebo to active treatment at Week 12 or Week 28 (in RAJ4). For subjects in each preceding study, following groups are defined:

Treatment Sequence Set for RAJ1

11 cutiment sequence set for 14 for											
Treatment Sequence	Treatment Sequence	initial treatment									
Code	Label	group									
SEQ J1-1	25mg	ASP015K 25mg									
SEQ J1-2	50mg	ASP015K 50mg									
SEQ J1-3	100mg	ASP015K 100mg									
SEQ J1-4	150mg	ASP015K 150mg									
SEQ J1-5	Placebo	Placebo									

- o 25 mg: subjects who initially treated as ASP015K 25 mg Group
- o 50 mg: subjects who initially treated as ASP015K 50 mg Group
- o 100 mg: subjects who initially treated as ASP015K 100 mg Group
- o 150 mg: subjects who initially treated as ASP015K 150 mg Group
- Placebo: subjects who initially treated as Placebo Group

Treatment Sequence Set for RAJ3

Treatment Sequence	Treatment Sequence	Week 0- Week 12	Week 12- Week 52
Code	Label		
SEQ J3-1	100mg	ASP015K 100 mg	ASP015K 100 mg
SEQ J3-2	150mg	ASP015K 150 mg	ASP015K 150 mg
SEQ J3-3	Placebo to 100mg at Week 12	Placebo	ASP015K 100 mg
SEQ J3-4	Placebo to 150mg at Week 12	Placebo	ASP015K 150 mg
SEQ J3-5	Etanercept	Etanercept	Etanercept

- o 100 mg: subjects who initially treated as ASP015K 100 mg Group
- o 150 mg: subjects who initially treated as ASP015K 150 mg Group
- Placebo to 100 mg at Week 12: subjects who initially treated as Placebo group and switched ASP015K 100 mg at Week 12 and at least one dose of ASP015K 100 mg drug after switched

- Placebo to 150 mg at Week 12: subjects who initially treated as Placebo group and switched ASP015K 150 mg at Week 12 and at least one dose of ASP015K 150 mg drug after switched
- Etanercept: subjects who initially treated as Etanercept Group. Subjects in this group do not shift to this study.

Treatment Sequence Set for RAJ4

Treatment Sequence Set 101 KA104						
Treatment	Treatment	Week 0- Week 12	Week 12- Week 28	Week 28- Week 52		
Sequence	Sequence Label					
Code						
SEQ J4-1	100mg	ASP015K 100 mg	ASP015K 100 mg	ASP015K 100 mg		
SEQ J4-2	150mg	ASP015K 150 mg	ASP015K 150 mg	ASP015K 150 mg		
SEQ J4-3	Placebo to 100mg at Week 12	Placebo	ASP015K 100 mg	ASP015K 100 mg		
SEQ J4-4	Placebo to 150mg at Week 12	Placebo	ASP015K 150 mg	ASP015K 150 mg		
SEQ J4-5	Placebo to 100mg at Week 28	Placebo	Placebo	ASP015K 100 mg		
SEQ J4-6	Placebo to 150mg at Week 28	Placebo	Placebo	ASP015K 150 mg		

- o 100 mg: subjects who initially treated ASP015K 100 mg
- o 150 mg: subjects who initially treated ASP015K 150 mg
- Placebo to 100 mg at Week 12: subjects who initially treated Placebo group and switched 100 mg at Week 12 and at least one dose of ASP015K 100 mg drug after switched
- Placebo to 150 mg at Week 12: subjects who initially treated Placebo group and switched ASP015K 150 mg at Week 12 and at least one dose of ASP015K 150 mg drug after switched
- Placebo to 100 mg at Week 28: subjects who initially treated Placebo group and switched ASP015K 100 mg at Week 28 and at least one dose of ASP015K 100 mg drug after switched
- Placebo to 150 mg at Week 28: subjects who initially treated Placebo group and switched ASP015K 150 mg at Week 28 and at least one dose of ASP015K 150 mg drug after switched
- If onset date of AE is Unknown, then missing onset date of AE will be imputed as following steps.
 - 1. If only the day of the month is missing (e.g., 2013-03), then the first day of the month will be used (2013-03-01),
 - 2. If both day and month are missing (e.g., 2013), then the first day of January will be used (2013-01-01).
 - 3. If day, month and year are missing, then the first date of study drug will be used.
 - 4. If imputed onset date of AE is earlier than the first date of study drug, [Adverse Events(From RAJ2) -page of the CRF]

then the onset date of AE will be re-imputed by the same date as the first date of study drug at RAJ2.

[Adverse Events(From RAJ1)/(From RAJ3 or RAJ4) -page of the CRF] then the onset date of AE will be re-imputed by the same date as the first date of study drug at the preceding study.

7.2 Study Population

These analyses will be also conducted for overall by Study Region.

7.2.1 Disposition of Subjects

[Analysis Set: All Subjects with Informed Consent]

The following subject data will be summarized and presented:

- Screened
- Screen failed
- Dosed

[Analysis Set: All Dosed Subjects]

The following subject data will be summarized and presented:

- Subjects who prematurely discontinued from the study period during overall period
- In addition, subjects who prematurely discontinued from the study period will be summarized for primary reason for withdrawal during overall period.
- Subjects who prematurely discontinued from the study period up to 84 months, each interval are as follows:
- In addition, subjects who prematurely discontinued from the study period will be summarized for primary reason for withdrawal up to 84 months
 - \circ 0 1 month
 - 1 <- 3 months
 - \circ 3 <- 6 months
 - 6 <- 12 months
 - 12 <- 24 months
 - o 24 <- 36 months
 - o 36 <- 48 months
 - o 48 <- 60 months
 - \circ 60 <- 72 months
 - o 72 <- 84 months
 - o 84 months <
- Subjects who included/excluded of FAS, SAF, and PDAS

• In addition, subjects who were excluded from FAS, SAF, and PDAS will be summarized by reason for exclusion

[Analysis Set: Subject who experienced dose decrease to 50 mg]

The following subject data will be summarized and presented:

- Subjects who prematurely discontinued from the study period during overall period
- In addition, subjects who prematurely discontinued from the study period will be summarized for primary reason for withdrawal during overall period.

